4. INTERIM ANALYSIS

4.1 Interim Analysis

There will be no interim efficacy analysis.

4.2 Independent Data Monitoring Committee

An independent data monitoring committee (IDMC) will be established to review safety data periodically per the IDMC charter. The first formal safety review will occur after approximately 30 patients have been randomized in total and received at least 1 cycle of study treatment, or 6 months after the first patient is randomized (whichever comes first).

Detailed information regarding the composition of the IDMC and IDMC procedures will be provided in the IDMC charter.

5. STATISTICAL METHODOLOGY

In general, summary tabulations will be presented that display the number of observations, mean, standard deviation, median, minimum, and maximum for continuous variables, and the number and percentage (of nonmissing) per category for categorical data, unless specified otherwise.

5.1 Sample Size Justification

Approximately 124 patients (approximately 62 patients per treatment arm) will be randomized to the study (124 patients are targeted for the ITT population). The sample size was calculated to provide 90% power to detect a 30% improvement in ORR4 in the brentuximab vedotin treatment group, assuming ORR4 for the MTX or bexarotene alone treatment group is 40%. This calculation is based on a 2-sided χ^2 test with a significance level of $\alpha = 0.05$, and a 10% dropout rate using nQuery Advisor 7.0. A minimum of 30 patients (15 per treatment arm) with pcALCL will be included in the study.

5.2 Randomization and Stratification

The randomization scheme will be generated by Millennium. Before dosing, a randomization number will be assigned to each patient. The randomization schedule will also include the study-specific identifiers (company name, protocol name, and protocol number) and the date and time the schedule was generated.

Patients will be randomized in an overall ratio of 1:1 to Arm 1 (brentuximab vedotin) or Arm 2 (physician's choice of MTX or bexarotene) using an interactive voice response system (IVRS), stratified by baseline disease diagnosis (MF or pcALCL).

5.3 Unblinding

This is an open-label study; investigators and patients will know their individual treatment assignment. However, aggregate efficacy results by treatment group will be blinded to the study team, investigators, patients, and IRF throughout the study conduct.

5.4 Data Handling

5.4.1 Methods for Handling Missing Data

All available efficacy and safety data will be included in data listings and tabulations. The relevance of missing sample data will be assessed. Data that are potentially spurious or erroneous will be examined according to standard data management operating procedures.

In general, missing data will be treated as missing, and no data imputation will be applied unless otherwise specified.

5.4.2 Definition of Baseline Values

Unless otherwise specified, the baseline value is defined as the value collected at the time closest to, but before, the start of study drug administration.

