		Screening ^a	Enrollment	Cycle 1 (21-Day Cycle)			Cycle 2 (21-Day Cycle)	Cycle 3-16 (21-Day Cycle)		EOT/ET	PTFU ^b	
	Cycle (C) Day (D) Visit Window	-28 to D1	Within 72 hours of first dose	C1 D1	C1 D2 & 4	C1 D3 & 5	C2 D1	Cx D1	Cx D16- 21	30 days (±2 days) after last dose	Minimum of 24 months	
Baseline	Informed consent	X	Randomization to Study Treatment Arm Arm 1 - brentuximab vedotin or Arm 2 - Methotrexate or Bexarotene									
	Inclusion/exclusion	X										
	Demographics	X										
	Medical history	X										
	Complete physical exam	X										
	Height	X										
	Weight ^c	X		X				X	X		X	
	Pregnancy test ^d	X		X				X	X			
Archived tissue ^e	X											
Safety Assessments	Vital signs ^f	X		X ^f				X	X		X	
	Physical exam including focused lymphoma assessment			X ^g				X	X		X	X
	ECOG performance status	X		X				X	X		X	
	Hematology/serum chemistry ^h	X						X	X		X	
	Urinalysis	X										
	12-lead ECG	X		X ⁱ								
	Immune reconstitution assessment ^l		X				X	X		X		
Disease Assessment	mSWAT and photography ^k	X	X				X	X	X	X	X	
	Circulating Sézary cells	X	X ^l					X ^l		X	X	
	FDG-PET ^m	X										
	CT ⁿ	X							X ⁿ	X ⁿ	X ⁿ	
	Quality of life assessments ^o		X				X	X		X	X	

Brentuximab vedotin (SGN-35)
Clinical Study Protocol C25001 Amendment 5, EudraCT: 2010-024215-14

	Cycle (C) Day (D) Visit Window	Screening ^a -28 to D1	Enrollment Within 72 hours of first dose	Cycle 1 (21-Day Cycle)			Cycle 2 (21-Day Cycle)	Cycle 3-16 (21-Day Cycle)		EOT/ET 30 days (±2 days) after last dose	PTFU ^b Minimum of 24 months	
				C1 D1	C1 D2 & 4	C1 D3 & 5	C2 D1	Cx D1	Cx D16- 21			
	Healthcare Utilization	X		X			X	X		X	X	
	Skin biopsy ^p (CD30 Expression)	X							X ^p	X ^p	X ^p	
	Biopsies for disease assessment ^q			X								
	Disease status/survival ^r								X	X	X	
Treatment	Brentuximab vedotin administration			X			X	X				
	Methotrexate administration ^s			X			X	X				
	Bexarotene administration ^t			Bexarotene is dosed once a day for the course of the study								
	Monitoring of concomitant medications and procedures		Recorded from screening through 30 days after the last dose of study drug.									
	Adverse event reporting ^u		Recorded from first dose of study drug through 30 days after the last dose of study drug.									
	Serious adverse events		Serious adverse events ^v will be collected from signing of the informed consent form through 30 days after the last dose of study drug									
PK/PD	PK sample ^w			X ^w	X ^w	X ^w		X ^w		X		
	CCI											

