	Immunogenicity ^y			X				X		X		
	CCI											

Abbreviations: CT = computed tomography; CTACK = cutaneous T cell-attracting chemokine; ECG = electrocardiogram; ECOG = Eastern Cooperative Oncology Group; ET = early termination; EOT = end of treatment; FDG = fluorodeoxyglucose; MRI = magnetic resonance imaging; mSWAT = modified severity weighted assessment tool; PD = pharmacodynamics; PET = positron emission tomography; PK = pharmacokinetics; PTFU = posttreatment follow-up; TARC = thymus and activation regulated chemokine.

Tests and procedures should be performed on schedule, but occasional changes are allowable (± 2 days) for holidays, vacations, and other administrative reasons. If extenuating circumstances prevent a patient from beginning treatment or completing a scheduled procedure or assessment within this time, the patient may continue the study only with the written permission of the project clinician.

a Screening must occur within 28 days prior to randomization.

b All treated patients without disease progression at EOT/ET will be followed for objective response every 12 weeks (± 2 weeks) for a minimum of 24

Brentuximab vedotin (SGN-35)
Clinical Study Protocol C25001 Amendment 5, EudraCT: 2010-024215-14

		Screening ^a	Enrollment	Cycle 1 (21-Day Cycle)			Cycle 2 (21-Day Cycle)	Cycle 3-16 (21-Day Cycle)		EOT/ET	PTFU ^b
	Cycle (C) Day (D) Visit Window	-28 to D1	Within 72 hours of first dose	C1 D1	C1 D2 & 4	C1 D3 & 5	C2 D1	Cx D1	Cx D16- 21	30 days (±2 days) after last dose	Minimum of 24 months

months after the EOT visit, and then every 6 months (± 1 month); or until progressive disease or study closure. All randomized patients will also be followed for survival every 12 weeks (± 2 weeks) for a minimum of 24 months after the EOT visit, then every 6 months (± 1 month) until patient withdrawal, death, or study closure.

- c Weight will be measured at screening, on Day 1 of each treatment cycle, and at EOT. The brentuximab vedotin dose will be adjusted for patients who experience a ≥ 10% change in weight from baseline

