6.9 Blinding and Unblinding

This is an open-label study; investigators and patients will know the individual treatment assignments. However, aggregate efficacy results by treatment group will be blinded to the study team, investigators, patients, and IRF, throughout the study conduct.

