8.1.2 Randomization and Stratification

The randomization scheme will be generated by Millennium. Prior to dosing, a randomization number will be assigned to each patient. The randomization schedule also includes the study specific identifiers (company name, protocol name, and protocol number) and the date and time the schedule was generated.

Patients will be randomized in an overall ratio 1:1 to Arm 1: brentuximab vedotin or Arm 2: physician's choice of methotrexate or bexarotene using an Interactive Voice

Brentuximab vedotin (SGN-35)**Clinical Study Protocol C25001 Amendment 5, EudraCT: 2010-024215-14**

Response/Interactive Web Response System (IVRS/IWRS), stratified by baseline disease diagnosis (pcALCL or MF).

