5.8.1 Primary Efficacy Endpoint

The primary endpoint of this study is ORR4 per IRF. ORR4 per IRF is defined as the proportion of patients achieving an objective response that lasts at least 4 months (i.e., duration from first response to last response is ≥ 4 months) on study as determined by an IRF. Patients whose first response occurs after the start of subsequent anti-cancer therapy but otherwise meet the primary endpoint criteria will be excluded. For objective response, a patient must achieve a CR or PR. The objective response will be considered maintained for patients with a previous CR who experience recurrent disease (i.e. Relapse) unless the criteria for progressive disease are met. Determination of objective response will be based on a GRS, which consists of skin evaluation (mSWAT assessment) by investigator, nodal and visceral radiographic assessment by IRF, and detection of circulating Sézary cells (MF only) by IRF. Skin evaluation is done at screening, before dosing on Day 1 of Cycles 1, 2, and 3, at the end of every cycle beginning at Cycle 3, EOT, and at post treatment follow-up visits. Radiographic and blood assessments are less frequent due to ethical and logistical considerations.

For patients without nodal or visceral involvement (as determined by baseline CT scans), CT scans will be performed at screening and:

- During the cycle following the first skin response, ideally corresponding to the confirmation of the skin response, and 6 cycles (a minimum or 4 months) after that confirmed skin response.
- If there is a question of new or progressive disease in the LN/viscera

For patients with baseline nodal/visceral disease, CT scans will be performed at screening and:

- At the end of Cycles 3, 6, 9, 12, and 15, and per the follow-up schedule until disease progression
- If there is a question of new or progressive disease in the LN/viscera
- At EOT if the previous CT scan was performed more than 8 weeks before EOT

A blood sample for Sézary cell enumeration in patients with MF will be collected at screening; at the end of Cycles 3, 6, 9, 12, and 15, at EOT, and per the follow-up schedule until progressive disease or study closure.

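### By the SAP's default rule, score-based skin PR and PD are measured against the investigator's Cycle 1 Day 1 mSWAT, which is scheduled after open-label randomisation

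*SAP*

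**What the plan says.** - **Baseline rule.** SAP 5.4.2, as a default that yields where another rule is specified: "the baseline value is defined as the value collected at the time closest to, but before, the start of study drug administration". Neither document sets a different baseline for mSWAT.
- **When skin is scored.** SAP 5.8.1: "Skin evaluation is done at screening, before dosing on Day 1 of Cycles 1, 2, and 3". Two scores therefore precede the first dose.
- **Order of events.** Schedule of Events, footnote a: "Screening must occur within 28 days prior to randomization". The Enrollment column, where randomisation sits, comes before Cycle 1 Day 1 and is timed "Within 72 hours of first dose". Protocol 8.1.2 adds: "Prior to dosing, a randomization number will be assigned to each patient".
- **Who scores, and what they know.** For the IRF-based primary endpoint, SAP 5.8.1 lists "skin evaluation (mSWAT assessment) by investigator, nodal and visceral radiographic assessment by IRF". Protocol 6.9: "This is an open-label study; investigators and patients will know the individual treatment assignments".
- **What the score is used for.** In Protocol Table 7-2, skin PR is clearance of 50% to 99% from baseline. Skin PD includes a rise of at least 25% from baseline and, after a CR or PR, a rise beyond the nadir plus half the baseline score. SAP 5.8.1 accepts that in patients with skin-only disease the global response score (GRS) rests essentially on the skin response.

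**The concern.** The skin score is a judgement made by an unblinded assessor, and the thresholds are ratios to its baseline value. A baseline scored too high in one arm makes skin PR easier and score-based skin PD harder in that arm for the rest of follow-up; a baseline scored too low does the reverse. A score taken before randomisation could not be influenced by the allocation. The plan collects one at screening, but the default rule passes over it. The baseline CT is a screening scan, so the component that dominates the GRS is the one without that protection. ORR4 (the primary endpoint) and PFS are at stake.

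**Working it through.** The plan attaches no figure to this point, so the check is first a trace through the documents and then the arithmetic of the thresholds. The planned 124 patients reproduces (56 per arm for 70% v 40%, 112 in total, 112/0.9 = 124.4) and does not depend on the baseline rule.

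**1. Which score is baseline?** The candidates are screening and Cycle 1 Day 1 pre-dose. The second is closer to first dose. Schedule of Events footnotes g and l waive the Cycle 1 Day 1 physical examination and Sézary sample when screening was within 4 days before randomisation. Footnote k, which covers mSWAT and photographs, has no such waiver. The default therefore selects Cycle 1 Day 1.

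**2. Is the arm known by then?** In the scheduled order, yes: screening, then randomisation within 72 hours of first dose, then Cycle 1 Day 1, in an open-label trial.

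**3. Which calls use this score?**

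| Call | Uses baseline mSWAT? |
|---|---|
| Skin PR (50% clearance) | Yes |
| Skin PD, 25% increase | Yes |
| Skin PD, loss of response (nadir plus 50% of baseline) | Yes |
| Skin CR (full clearance), global CR | No |
| Skin PD by new tumours (MF) | No |
| Nodal, visceral and blood PD | No |
| Global PR through skin CR with disease elsewhere | No |

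The loss-of-response limb also applies after a CR. SAP 5.8.1 treats a response as maintained through relapse until PD criteria are met. So the 4-month duration can depend on the baseline score even in a complete responder, although the CR rate does not.

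**4. Would a planned analysis reveal a shift?** The sensitivity analyses in SAP 5.8.1.1 and 5.8.2.1.1 vary the population, assessor, response criteria, censoring, progression dating, and timing of CT and blood results. None is stated to vary the skin baseline. Agreement between IRF and investigator (SAP 5.8.1.2) cannot show it, because under SAP 5.8.1 both rest on the investigator's skin evaluation.

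**5. How far would the thresholds move?** Assumption: recorded baseline = f × true baseline, with later scores accurate.
- True fall needed for skin PR: 1 − 0.5f
- True rise needed for the 25% PD limb: 1.25f − 1
- Loss-of-response bar, for a true baseline of 100 and a nadir of 20 (example values): 20 + 50f

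| f | Fall for PR | Rise for PD | Loss-of-response bar |
|---|---|---|---|
| 0.90 | 55.0% | 12.5% | 65.0 |
| 1.00 | 50.0% | 25.0% | 70.0 |
| 1.05 | 47.5% | 31.3% | 72.5 |
| 1.10 | 45.0% | 37.5% | 75.0 |
| 1.20 | 40.0% | 50.0% | 80.0 |

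**6. Scale of consequence, if ORR4 did shift.** Assumptions: true ORR4 of 40% in both arms, 62 per arm, unstratified chi-square test, exact enumeration. The chance of a false win for brentuximab vedotin is 2.7% with no shift. It becomes 5.7%, 8.9% or 21.8% if that arm's recorded ORR4 is raised by 3, 5 or 10 points. These figures say what a shift would do, not that one of that size occurs.

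**The case against.** The last value before dosing is a usual and defensible baseline. Screening may be up to 28 days before randomisation, a 3-week washout applies (inclusion criterion 10), and the screening biopsies follow the screening mSWAT (Protocol 7.4.9). A screening baseline would therefore count some pre-treatment skin change as response or progression. This stands against simply switching to the screening score. It does not stand against a fresh score taken just before randomisation.

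Other parts of the objection also stand:
- If an investigator over-scores follow-up by the same proportion, the ratio is unchanged and no bias results.
- The rule is a default that yields to a specification elsewhere; an IRF charter, not among these documents, might provide one.
- The 72 hours is an outer limit. Scoring on Cycle 1 Day 1 and then randomising the same day is not forbidden, so a reader who infers that every baseline score is taken with the arm known goes beyond the documents.
- Photographs are taken at screening and Cycle 1 Day 1 and go to central review (Protocol 7.4.17.1.2). A reader might infer that a shift could never be found or corrected. The screening scores and photographs are material for finding one; what is missing is a rule for using them.

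A reader might also infer that every response and progression call, including CR, is affected. Table 7-2 and the GRS definitions (Protocol Table 7-6) do not support that, as step 3 shows.

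**Conclusion.** The concern holds in a limited form. Under the SAP's default, the reference for every score-based skin PR and skin PD call is an investigator score that the schedule places after open-label randomisation, although a pre-randomisation score exists. ORR4 and PFS are exposed, mainly in skin-only patients. No documented rule lets the IRF replace the skin score, and no planned analysis tests the choice.

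The size is known only for the thresholds. A 10% over-score, with accurate later scores, moves the true clearance needed for skin PR from 50% to 45% and the 25% PD limb to a true rise of 37.5%. The documents give neither the direction nor the amount of any bias.

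It is tempting to convert this into points of ORR4: if 5% of patients had a true clearance of 45% to 50%, about 3 of 62 (0.05 × 62 = 3.1) would cross the line. The documents do not support that step. They give no distribution of clearance, and crossing the threshold once is not ORR4: the response must be confirmed in skin at the next cycle and last at least 4 months. The change in ORR4 cannot be stated. The change should still be made, because it is cheap and closes a route to bias in the primary endpoint.

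**What to change.** 1. In SAP 5.4.2, define baseline mSWAT as the last score before randomisation. This also gives a baseline to ITT patients who are randomised but never dosed, for whom a dose-anchored rule is undefined.
2. Instruct sites to complete the pre-dose mSWAT and photographs before the IVRS/IWRS call. The reference stays recent and is fixed before the arm is known.
3. For patients already randomised, add a sensitivity analysis of ORR4 and PFS with the screening mSWAT as baseline, and report the change in mSWAT from screening to Cycle 1 Day 1 by arm. A difference between arms in that change would be a direct warning sign.

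Cost: one line in SAP 5.4.2, one added analysis and one summary on data already collected, and a visit-order constraint for sites. No further assessment is needed. In the sensitivity analysis the reference may be up to about 4 weeks old and precedes the screening biopsy, so it should support the primary analysis rather than replace it.

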5.4.3 Windowing of Visits

All data will be categorized based on the scheduled visit at which they were collected. These visit designators are predefined values that appear as part of the visit tab in the electronic case report form (eCRF).

5.4.4 Justification of Pooling

All data from all sites will be pooled. Study center or treatment-by-center interaction will not be included in any statistical analysis due to the rarity of the disease and potentially limited number of patients at each center.

5.4.5 Withdrawals, Dropouts, Loss to Follow-up

No dropouts will be replaced in this study.

5.5 Patient Disposition

The disposition of patients includes the number and percentage of patients for the following categories: patients treated (safety population), patients in the ITT population, patients in the All-Enrolled population, patients in the PP population, patients in the Response-Evaluable population, patients in the PK and Pharmacodynamics populations, patients completed, and patients discontinued from the study. All percentages will be based on the number of patients randomized.

The primary reason for study and treatment discontinuation will also be summarized in this table.

A listing will present data concerning patient disposition.

5.6 Demographics and Baseline Disease Characteristics

5.6.1 Demographics

Demographic and baseline characteristics will be summarized by treatment groups. Baseline demographics and baseline characteristics to be evaluated will include age, gender, race, height, weight, body surface area (BSA), primary diagnosis (stratification factor), Eastern Cooperative Oncology Group (ECOG) performance status (0, 1, 2), and other parameters as appropriate.

No inferential statistics will be generated.

5.6.2 Medical History

General medical history and prior medications will be listed for all patients.

5.7 Treatments and Medications

5.7.1 Concomitant Medications

Concomitant medications will be coded by generic term using the 2002 version of the World Health Organization (WHO) Drug Dictionary. The number and percentage of normal subjects taking concomitant medications from screening through the end of the on-study period will be tabulated by Anatomical Therapeutic Chemical (ATC) classification pharmacological subgroup and WHO drug generic term.

Concomitant procedures will not be coded but will be presented in a data listing.

5.7.2 Study Treatments

Patients will be randomized to receive study treatment, either brentuximab vedotin or bexarotene or MTX.

Brentuximab vedotin will be administered by outpatient intravenous (IV) infusion given over approximately 30 minutes on Day 1 of each 21-day cycle. The dose of brentuximab vedotin is 1.8 mg/kg. Study treatment will be administered through a dedicated IV line and cannot be mixed with other medications. Details on the dosing of study drug can be found in the protocol.

MTX will be given once weekly as a single dose of 5 to 50 mg orally. Dosages may be gradually adjusted to achieve optimal clinical response but must not exceed 50 mg/week. Once optimal clinical response is achieved, the MTX dosage should be decreased to the lowest effective dose. For patients deriving benefit, MTX dosing should be continued up to 48 weeks.

The recommended initial dose of bexarotene capsules is 300 mg/m²/day. Bexarotene capsules should be taken as a single oral daily dose with a meal. Bexarotene capsules should be continued as long as the patient is deriving benefit, up to 48 weeks. All patients (with normal or normalized triglyceride levels) who are to be given bexarotene should receive 7 days of pretherapy with fenofibrate 145 to 200 mg daily starting from Cycle 1 Day 1 (i.e., the initial dose of bexarotene starts on Day 8 of Cycle 1).

5.7.2.1 Extent of Exposure

The exposure to study drug will be characterized by total amount of dose taken in mg, total number of dose taken, number of treated cycles, duration of treatment, numbers and percentages of patients in treated cycle categories (1, 2...,16), and dose intensity (mg/week). Dose intensity (mg/week) will be calculated as total dose administered (mg)/(3 * number of treated cycles) where a treated cycle is defined as a 21-day period during which the patient received any amount of brentuximab vedotin (scheduled for a single dose in a 21-day cycle), MTX (single weekly dose), or bexarotene (single oral daily dose). The duration of treatment is defined as time from the first study dose to 21 days after the last study dose ([last dose date + 21] – first dose date) of brentuximab vedotin, or time from the first study dose to 7 days after the last study dose ([last dose date + 7] – first dose date) of MTX, or time from the first study dose to 1 days after the last study dose ([last dose date + 1] – first dose date) of bexarotene.

Relative dose intensity (%) will be calculated as (Total Dose Administered/Total Dose Expected) * 100 and summarized by treatment group.

All extent-of-exposure data will be summarized as continuous variables for brentuximab vedotin, methotrexate, and bexarotene in the safety population. Study drug administration and exposure information will also be presented in a by-patient data listing.

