6.4.1 Criteria for Beginning or Delaying a Subsequent Treatment Cycle

Treatment with brentuximab vedotin or reference therapy will use a cycle length of 21 days. For a new cycle of treatment to begin, the patient must meet the following criteria:

- ANC must be $\geq 1,000/\text{mm}^3$
- All other study drug-related toxicity must have resolved per the guidelines provided in [Table 6-3](#) and [Table 6-4](#).

If the patient fails to meet the criteria for retreatment cited previously, initiation of the next cycle of treatment should be delayed up to 1 week. At the end of that time, the patient should be re-evaluated to determine whether the criteria for retreatment have been met. The start of the next cycle may be delayed for up to 3 weeks if additional time is required for the patient to recover from study treatment-associated toxicity experienced during the current cycle. Delays of greater than 3 weeks are prohibited without approval of the sponsor.

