6.4.2 Criteria for Dose Reduction

Brentuximab vedotin

Inpatient dose reduction to 1.2 mg/kg brentuximab vedotin will be allowed depending on the type and severity of toxicity. Please refer to [Table 6-3](#) and [Table 6-4](#) for further information.

When a dose reduction of brentuximab vedotin is required, no re-escalation of dose will be permitted.

Reference Therapy

Please refer to Section 6.2 for drug-specific dose reduction guidelines for methotrexate and bexarotene, respectively.

Brentuximab vedotin (SGN-35)

Clinical Study Protocol C25001 Amendment 5, EudraCT: 2010-024215-14

Table 6-3 Recommended brentuximab vedotin Dose Modifications for Treatment-Associated Toxicity Excluding Neuropathy

Toxicity	Grade 1	Grade 2	Grade 3	Grade 4
Non-hematologic (excluding neuropathy)	Continue at same dose level.	Continue at same dose level.	Withhold dose until toxicity is \leq Grade 1 or has returned to baseline, then resume treatment at the same dose level ^a .	Withhold dose until toxicity is \leq Grade 1 or has returned to baseline, then reduce dose to 1.2 mg/kg and resume treatment, or discontinue at the discretion of the investigator after discussion with the sponsor. ^a
Hematologic	Continue at same dose level.	Continue at same dose level.	Withhold dose until toxicity is \leq Grade 2, or has returned to baseline, then resume treatment at the same dose level ^b . Consider growth factor support (G-CSF or GM-CSF) for treatment of neutropenia and prophylaxis in subsequent cycles.	Withhold dose until toxicity is \leq Grade 2, then resume treatment at the same dose level. Consider growth factor support (G-CSF or GM-CSF) for treatment of neutropenia and prophylaxis in subsequent cycles. For the second occurrence of Grade 4 toxicity (if neutropenia, while receiving growth factor support), withhold dose until toxicity is \leq Grade 2, then reduce the dose to 1.2 mg/kg and resume treatment after discussion with the sponsor. ^b

Grading based on National Cancer Institute (NCI) Common Terminology Criteria for Adverse Events (CTCAE) v. 4.03

a Patients who develop Grade 3 or 4 electrolyte laboratory abnormalities may continue study treatment without interruption. Brentuximab vedotin will be held for clinically meaningful Grade 3 or 4 electrolyte abnormalities.

b Patients who develop Grade 3 or 4 lymphopenia may continue study treatment without interruption.

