Table 6-4 Recommended brentuximab vedotin Dose Modifications for Treatment-Emergent or Worsening Peripheral Sensory or Motor Neuropathy

Severity of Peripheral Sensory or Motor Neuropathy (Signs and Symptoms [abbreviated description of CTCAE])	Modification of Dose and Schedule
Grade 1 (Asymptomatic; clinical or diagnostic observations only; intervention not indicated; paresthesia and/or loss of deep tendon reflexes)	Continue with the same dose and schedule
Grade 2 (Moderate symptoms; limiting instrumental activities of daily living)	Withhold dose until toxicity returns to \leq Grade 1 or baseline, then restart treatment at a reduced dose of 1.2 mg/kg every 3 weeks
Grade 3 (Severe symptoms; limiting self care activities of daily living)	
Grade 4 (life-threatening consequences; urgent intervention indicated)	Discontinue treatment
Grade 5 (Death)	

Grading based on National Cancer Institute (NCI) Common Terminology Criteria for Adverse Events (CTCAE) v. 4.03; see neuropathy; peripheral motor neuropathy; peripheral sensory neuropathy.

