5.7.2.2 Treatment Modifications

Action on study drug (including dose reduction) will be summarized by treatment group, by cycle, and overall.

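### Brentuximab vedotin dose intensity is labelled mg/week but counts every treated cycle as 3 weeks, so dose delays without reduction leave it unchanged

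*SAP*

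**What the plan says.** SAP 5.7.2.1 gives the formula: "Dose intensity (mg/week) will be calculated as total dose administered (mg)/(3 * number of treated cycles". It adds that "a treated cycle is defined as a 21-day period during which the patient received any amount of brentuximab vedotin", which is "scheduled for a single dose in a 21-day cycle"; parallel wording covers weekly methotrexate (MTX) and daily bexarotene.

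The same paragraph defines an elapsed-time variable that the dose intensity formula does not use. For brentuximab vedotin: "The duration of treatment is defined as time from the first study dose to 21 days after the last study dose". For MTX and bexarotene the addition after the last dose is 7 days and 1 day. Relative dose intensity is administered over expected total dose, as a percentage, and the expected total is not defined.

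On delays, Protocol 6.4.1 says: "The start of the next cycle may be delayed for up to 3 weeks if additional time is required". In Protocol 6.4.2, Table 6-3 includes toxicities for which the dose is withheld and the instruction is "then resume treatment at the same dose level". For Grade 2 and 3 neuropathy, Table 6-4 says to withhold, "then restart treatment at a reduced dose of 1.2 mg/kg every 3 weeks".

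SAP 5.7.2.2 adds: "Action on study drug (including dose reduction) will be summarized by treatment group, by cycle, and overall".

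**The concern.** A figure in mg/week will be read as drug delivered per calendar week. Under this formula a late infusion adds no treated cycle, and the extra weeks before it are not counted. A patient managed by delay alone therefore shows the planned rate, however late the infusions were. A patient who is both delayed and reduced shows the reduction but not the delay.

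Exposure is the background against which toxicity is interpreted. A weekly rate that ignores delay makes delivery of brentuximab vedotin look closer to plan than it was, to an extent that depends on how often delays occur. Relative dose intensity may or may not make up for this: because the expected total is undefined, the reader cannot tell whether it reflects delay.

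**Working it through.** The SAP states no dose intensity value, so there is no figure to reproduce. The inputs are the formula and the treated-cycle and duration definitions (SAP 5.7.2.1), the 1.8 mg/kg dose (SAP 5.7.2), the maximum of 16 cycles or 48 weeks (SAP 1.1), the permitted delay (Protocol 6.4.1) and the 1.2 mg/kg reduced dose (Protocol 6.4.2). Body weight (80 kg) and the delay patterns are assumptions.

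**Consistency without delay.** The cycle count gives 16 × 3 = 48 weeks. The SAP's duration definition gives 15 × 21 + 21 = 336 days = 48 weeks. The two denominators agree when every cycle lasts 21 days.

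**With delay.** Take n infusions of d mg and D weeks of delay between the first and last infusions.

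- As written: d·n / (3n) = d/3. Neither n nor D remains.
- Over elapsed weeks: d·n / (3n + D).
- Overstatement: (3n + D)/(3n) − 1 = D/(3n), whatever the weight or dose.

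At 80 kg a full dose is 1.8 × 80 = 144 mg.

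| Pattern (assumed) | As written, mg/week | Elapsed time, mg/week | Overstatement |
|---|---|---|---|
| 16 doses, no delay | 2304/48 = 48.0 | 2304/48 = 48.0 | 0% |
| 16 doses, 1 week in total | 48.0 | 2304/49 = 47.0 | 1/48 = 2.1% |
| 16 doses, 4 weeks in total | 48.0 | 2304/52 = 44.3 | 4/48 = 8.3% |
| 8 doses, one 3-week delay | 1152/24 = 48.0 | 1152/27 = 42.7 | 3/24 = 12.5% |
| 16 doses, 8 weeks in total | 48.0 | 2304/56 = 41.1 | 8/48 = 16.7% |

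**Delay with reduction.** Suppose a 3-week delay, then 1.2 mg/kg (96 mg) from dose 9 of 16. Total dose is 8 × 144 + 8 × 96 = 1920 mg. As written this is 1920/48 = 40.0 mg/week; over elapsed time it is 1920/51 = 37.6. The reduction is captured, the delay is not, and the overstatement is 3/48 = 6.3%.

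**Reading of the 21-day period.** It could start at each infusion or run as consecutive calendar windows from Day 1. In every delay pattern tested, both readings gave one treated cycle per infusion and the same result.

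**The case against.** The best defence is that the statistic is transparent. The denominator is stated where the label appears, so a careful reader knows it is a rate per treated cycle in weekly units. No exposure information is lost either: total dose, number of doses and duration of treatment are all summarised, actions on study drug are tabulated by cycle, and a by-patient listing is planned. An elapsed-time rate could be rebuilt from these.

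The typical effect may also be small. Protocol 1.3 reports Grade 3 and 4 neutropenia in 13% and 7% of phase 2 patients, usually short and handled with brief delays. If 20% of patients had one 1-week delay over 8 doses, the mean overstatement would be 0.20 × 1/24 = 0.8%. Table 6-4 pairs withholding for Grade 2 and 3 neuropathy with a reduction, which the statistic does register. In the reduction example above, most of the fall comes from the reduction (48.0 to 40.0) rather than the uncounted delay (40.0 to 37.6).

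These points limit the consequence. The 0.8% is itself an assumed scenario covering one toxicity; other toxicities add to it and individual patients can exceed it. Stating the denominator does not make mg/week true, and a reader should not have to rebuild the rate that the label already claims to give. The undefined expected dose is a separate gap and is not evidence that the formula is wrong.

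**Conclusion.** The concern holds. For brentuximab vedotin the statistic is mean dose per infusion divided by 3. It responds to dose reductions but not to delays, and it is a weekly rate only when every cycle lasts exactly 21 days. That follows from the SAP's definitions and needs no assumption.

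The size does need one. The overstatement is D/(3n), from 0% with no delay to 16.7% in the most delayed pattern tabulated; heavier delay would give more. The trial-wide average cannot be derived from the documents. The consequence is confined to a descriptive summary in the safety population. It is worth correcting because a reported figure would not mean what its unit says.

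**What to change.** In SAP 5.7.2.1, compute dose intensity as total dose administered (mg) divided by duration of treatment in weeks, using the per-drug duration already defined there: (last dose date + 21, 7 or 1 days − first dose date) / 7. Using it for all three drugs is sound, because whole-cycle counting also misstates weeks for a partial cycle; SAP 5.7.2, for example, starts bexarotene on Day 8 of Cycle 1. If the present statistic is kept, label it as mean mg per treated cycle divided by 3.

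For brentuximab vedotin, express relative dose intensity as the elapsed-time mg/week over the planned mg/week (planned dose per 3 weeks). State separately what the expected total dose means for MTX, which is titrated within 5 to 50 mg and has no fixed planned dose, and for bexarotene.

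One limit remains: withholding after a final dose that is never followed by another still does not enter the duration.

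The cost is one changed denominator and three written definitions, with no new data. Where delays occur, reported brentuximab vedotin dose intensity will be somewhat lower.
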